### ***Severe and life-threatening bleeding episodes***

From a patient safety perspective, specific recommendations for the management of severe and life-threatening bleeding episodes (see definition in [Table 10](#) in the protocol) are not considered feasible as such management often poses several complex clinical challenges that need to be addressed case by case by the treating physicians hereby tailoring and securing the optimal treatment, which in some cases may be high factor replacement doses for extended periods of time. In the rare event of a severe (life-threatening) bleed the patient should be in immediate and close contact to the investigator and be treated with relevant doses of factor containing products at the discretion of the investigator.

### ***Investigator–patient interactions and training***

It is important that patients are trained in the management of bleeds. New and updated training material for both site staff and patients has been developed, see overview in [Table 23](#).

**Table 23      Overview of documents for investigator and patient training.**

| Investigators & Site Staff                                         | Patients                                                                                                                                                         |
|--------------------------------------------------------------------|------------------------------------------------------------------------------------------------------------------------------------------------------------------|
| Patient bleed treatment plan
Guidance for management of bleeds. | Updated Informed Consent Forms
Updated Patient Handbook
Trial ID patient card – key instructions to the patient on how to proceed when suspecting a bleed. |

### ***Patient-specific bleed treatment plan***

Investigative sites are encouraged to create a patient-specific plan for breakthrough bleed treatment such that all involved investigators are aligned in the treatment instructions to the patient when the patient contacts the site.

### ***Patient education on management of bleeds***

Adequate management of breakthrough bleeds is important for the patient's safety and overall disease outcome, and to the outcome of the trial. The investigator must educate the patient on adequate management of bleeds before (re-)start of concizumab treatment (i.e., visit 2a (arms 2–4) or visit 9a (arm 1)). The training conversation with the patient must be documented in the patient medical records and should as a minimum cover the below points:

- Introduce management of bleeds during concizumab prophylaxis as described in Sections [5.2.2](#) and [9.2.2](#)
- Explain need for a cautious treatment approach while avoiding undertreatment
- Provide rationale to the patient for a close patient to site contact
- Instruct patients to contact site before every bleed treatment dose
- Discuss practicalities of contacts to the investigational site i.e. when, how and whom to contact
- Describe to the patient the difference between traumatic and spontaneous bleed
- Discuss severe bleeds and surgical procedures with the patient
- Explain what products the patient should use for treatment of bleeds and how
- Touch on dose levels and intervals between dosing

- Explain how to record bleeds and bleed treatment in the eDiary
- Introduce the patient information material and explain how to use it.

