| Number of treated spontaneous bleeding episodes                 | 
On demand (arm 1)
 
 
From randomisation (week 0) up until start of concizumab treatment (at least 24 weeks)
 
 
Concizumab (arm 2)
 
 
From start of the new concizumab dosing regimen (week 0) up until the primary analysis cut-off (at least 32 weeks)
 
                                                                                                                                                                                                                                                          | Count |
| Number of treated spontaneous and traumatic joint bleeds        | 
On demand (arm 1)
 
 
From randomisation (week 0) up until start of concizumab treatment (at least 24 weeks)
 
 
Concizumab (arm 2)
 
 
From start of the new concizumab dosing regimen (week 0) up until the primary analysis cut-off (at least 32 weeks)
 
                                                                                                                                                                                                                                                          | Count |
| Number of treated spontaneous and traumatic target joint bleeds | 
On demand (arm 1)
 
 
From randomisation (week 0) up until start of concizumab treatment (at least 24 weeks)
 
 
Concizumab (arm 2)
 
 
From start of the new concizumab dosing regimen (week 0) up until the primary analysis cut-off (at least 32 weeks)
 
                                                                                                                                                                                                                                                          | Count |

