### **9.2.1 eDiary**

Novo Nordisk will provide the patient with an eDiary for electronic recording of following assessments:

- Treatment with concizumab, see Section [9.2.2](#)
- Bleeding episodes including treatment of bleeds, see Section [9.2.3](#)

- PRO questionnaires see Section [9.2.6](#)
- Health economic questions see Section [9.8](#)

The eDiary and related support services will be supplied by a vendor working under the direction and supervision of Novo Nordisk.

Patients or patient's caregiver will be trained in the use of the eDiary by the investigator or delegated personnel before entering of any data. The eDiary will be dispensed to the patient at visit 2a (unless an eDiary has already been dispensed). After visit 2a and onwards, data will be entered by the patient or patient's caregiver in the eDiary at home. The patient should bring his eDiary at all visits to ensure the eDiary is working properly. The eDiary will be returned by the patient at the end of trial visit (visit 27a).

For data collected in the eDiary, the investigator must review treatment data, bleeding episodes and specific PRO's, as specified in Section [9.2.6](#). The review should be documented accordingly. It is the responsibility of the investigator to instruct the patient about the timelines for timely completion of the eDiary.

If the investigator finds it necessary to amend or correct eDiary data, the patient must be consulted, and outcome documented prior to requesting the actual data change. A Data Correction Request must be submitted to the eDiary vendor. An audit trail will be maintained.

All data entered will be transferred from the eDiary to an electronic database, where it is kept as a certified copy of the source data by the eDiary vendor. Data entered in the eDiary will upon confirmation of a successful back-up be deleted from the eDiary.

The eDiary will have built in edit checks and reminders, to ensure that all relevant questions are answered. eDiary data transferred to the electronic database will be viewable to relevant trial site staff and Novo Nordisk personnel on a secure, password protected web portal.

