**Table 9 Definitions of bleeding episodes (cause of bleed)**

| Category             | Definition                                                                                                                |
|----------------------|---------------------------------------------------------------------------------------------------------------------------|
| Spontaneous   | Not linked to a specific, known action or event                                                                           |
| Traumatic     | Caused by a specific, known action or event (e.g. injury or exercise)                                                     |
| Post-surgical | Bleeding episodes after surgery from the surgical wound. Bleeding episodes during surgery do not fall under this category |

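### The mandated teaching on traumatic versus spontaneous bleeds precedes arm 2's window but falls at the end of arm 1's, leaving the supportive spontaneous-bleed comparison open to differential misclassification

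*Protocol*

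**What the plan says.** **Teaching.** Protocol Appendix 11, under patient education on management of bleeds, makes the investigator hold and document a training conversation. Its timing is given as "before (re-)start of concizumab treatment (i.e., visit 2a (arms 2–4) or visit 9a (arm 1". The minimum content includes "Describe to the patient the difference between traumatic and spontaneous bleed".

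**Endpoint.** Section 4.3.2.2 lists "Number of treated spontaneous bleeding episodes" as a supportive secondary endpoint. The arm 1 window is "From randomisation (week 0) up until start of concizumab treatment (at least 24 weeks" and the arm 2 window is "From start of the new concizumab dosing regimen (week 0) up until the primary analysis cut-off (at least 32 weeks". The note to Table 1 in section 5.1 places arm 1's concizumab start at visit 9a.

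**Recording of cause.** Section 9.2.3 makes cause a required item for every bleed. Home-treated bleeds go into the eDiary and site-treated bleeds into the eCRF. That section and Appendix 11 assign severity to the investigator; neither assigns cause. Table 9 defines a traumatic bleed as "Caused by a specific, known action or event (e.g. injury or exercise" and a spontaneous bleed as one with no such link.

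**Provisions common to both arms.** Under section 9.2.1, patients or caregivers "will be trained in the use of the eDiary by the investigator or delegated personnel before entering of any data", and the investigator reviews diary bleeds. The section 2 flowchart has patient material handed out at visit 1a.

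**The concern.** In an open-label trial, the only instruction on cause that the protocol expressly mandates reaches the two randomised arms at different points of their comparison windows. Arm 2 patients on the new regimen receive it before their first counted bleed. Arm 1 patients need not receive it until on-demand follow-up of at least 24 weeks is ending.

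The rule being taught is not self-evident, since a bleed brought on by exercise counts as traumatic. If instruction changes how patients label such bleeds, the arms would be applying different working definitions. The spontaneous rate ratio could then move with no change in bleeding. Section 5.5.1 of the week-56 SAP also tabulates bleeds by cause. There, arm 1's on-demand column would be the one recorded before the mandated teaching.

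**Working it through.** **1. Timing, side by side**

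| | Arm 1, on demand | Arm 2, new regimen |
|---|---|---|
| Window opens | randomisation | start of new regimen, visit 2a |
| Mandated teaching on cause | visit 9a, before concizumab | visit 2a, before concizumab |
| Window closes | start of concizumab, visit 9a | primary analysis cut-off |

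The teaching comes before all of arm 2's new-regimen window and after essentially all of arm 1's. Two groups need separate mention:
- Arm 1 patients randomised before the pause re-enter at visit 9a (section 5.1, Table 1) and are expected to have completed at least 24 weeks by then. Teaching at visit 9a cannot reach those data.
- Arm 2 patients who did not restart contribute time on the initial regimen (section 10.3.1). No visit 2a conversation precedes their window.

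**2. The plan's own figure.** Section 10.1 gives at least 88% power for ABR 18 versus 5, yearly over-dispersion 13, 14 versus 28 patients, and 24 versus 32 weeks. A check with 10,000 simulated trials per cell used gamma-Poisson counts, a negative binomial model and a two-sided 95% Wald interval. It gave 87.4%. All 15 cells of Table 16 agreed within 1.0 percentage point. The withdrawal allowance also reproduces: 42/(1 − 0.17) = 50.6, rounded up to 51.

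**3. Effect on the primary endpoint.** With S spontaneous and T traumatic treated bleeds, relabelling k of them gives (S − k) + (T + k) = S + T. The pooled count and the power above do not change.

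**4. Effect on the spontaneous count.** The documents give no spontaneous share and no error rate, so every input here is an assumption. Let s be the true spontaneous share in arm 1, a the fraction of spontaneous bleeds recorded as traumatic, and b the fraction of traumatic bleeds recorded as spontaneous. Take arm 2 as error-free.

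Arm 1 observed/true = [s(1 − a) + (1 − s)b]/s, and the arm 2/arm 1 spontaneous rate ratio is multiplied by the inverse. Over s = 0.5 to 0.9:

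- a = 0.10 to 0.20, b = 0: 1/0.90 = 1.11 to 1/0.80 = 1.25, against concizumab.
- a = 0, b = 0.10 to 0.30: weakest at s = 0.9, b = 0.10, where (0.90 + 0.01)/0.90 = 1.011 gives 0.99. Strongest at s = 0.5, b = 0.30, where (0.50 + 0.15)/0.50 = 1.30 gives 0.77. Both favour concizumab.
- a = b: 1.00 at s = 0.5. At s = 0.9 and 20% each way, (0.72 + 0.02)/0.90 = 0.822 gives 1.22.

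**5. On the ratio scale.** The documents give no planning ratio for spontaneous bleeds. Borrowing the all-treated-bleeds ratio 5/18 = 0.278, the extremes are 0.278 × 0.77 = 0.21 and 0.278 × 1.25 = 0.35.

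**The case against.** The strongest reply is that silence is not asymmetry. Appendix 11 is a pre-concizumab safety checklist. It also lists explaining how to record bleeds in the eDiary, which section 9.2.1 already gives every patient before data entry, so its items need not be new to arm 1 at visit 9a. Cause is a required field with one definition for all arms, and training on the diary may well cover it. The investigator reviews diary bleeds, and section 9 has discrepancies clarified with the patient. Sites already handle the distinction when taking bleed history and target joints (sections 9.1.3 and 9.1.4). The Patient Handbook and diary training material are not among the documents and might teach it.

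Much of this stands, and it limits what can be claimed. A reader might infer that arm 1 patients went untaught, or were taught only after their window closed. Neither is supported: the teaching is due before concizumab starts, so at or just before the close, and earlier instruction is not excluded. A reader might also infer that the bias favours concizumab. Nothing in the documents fixes its direction.

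What the reply does not supply is any provision requiring arm 1 to be taught the Table 9 definitions at visit 2a, or requiring anyone to check recorded cause against them. General review of diary bleeds is not that check.

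**Conclusion.** The point holds as a modest design weakness. The protocol's arm-specific timing leaves the supportive comparison of treated spontaneous bleeds, and the week-56 tables by cause, open to differential misclassification of unknown direction and size. The multipliers of 0.77 to 1.25 illustrate what assumed error rates would do; they are not estimates. They also treat every arm 1 bleed as exposed to the error. Bleeds classified at the site, or patients taught earlier, would shrink the effect. That home-treated patients enter cause themselves is a reading of section 9.2.3, which assigns several other items to the site but not this one.

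It would be wrong to infer that the primary result is at risk, because that endpoint counts both causes together. The spontaneous count is outside the testing hierarchy in section 10.3, and the week-56 SAP tests no hypotheses. The SAP for the primary analysis cut-off, which governs the secondary endpoints, was not available for this review. Even at the illustrated extremes the borrowed ratio would still show a large reduction. The case for acting is that the asymmetry comes from the protocol's own scheduling and is cheap to remove.

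**What to change.** In Appendix 11, add a sentence requiring the Table 9 explanation of traumatic and spontaneous bleeds at visit 2a for all arms, including arm 1, when the eDiary is handed out. Keep the concizumab-specific items at visit 9a for arm 1.

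Do not relabel cause retrospectively in arm 1 on-demand data already collected. That would rest on recall over 24 weeks or more and on unblinded judgement, and could add bias of its own. Instead, when reporting the spontaneous-bleed comparison and the by-cause tables, state that the mandated instruction on cause was timed differently in the two randomised arms.

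The cost is a few minutes at a visit already held. No sample size, visit or analysis changes. The remaining downside is that arm 1 data recorded before the change stay without the mandated instruction.

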### ***Investigator's responsibilities regarding patient information material***

The investigator must hand out all approved supportive material to the patient for him to bring home. The purpose of the patient information material is to help the patient remember trial instructions and procedures, as well as to serve as documentation.

Furthermore, the investigator has the following responsibilities:

- Provide information to the patient in accordance with the latest version of the informed consent form, particularly Section 5 'What are the possible side effects or harms of taking part?'.
- Hand out the Patient Handbook to the patient and ensure that the patient is familiar with the content of the current version of the Patient Handbook to an extent that allows the patient to comply with the trial procedures. The Patient Handbook is developed as a tool for patients describing the trial and the connected trial procedures in layman terms, and it is recommended to put emphasis on following sections:
  - Bleeds
  - Treatment of bleeds
  - Thromboembolic events
  - Electronic Diary
- Hand out the Trial ID patient card, which carries key instructions to the patient on how to proceed when suspecting a bleed.

### ***Investigator's responsibilities concerning reporting of bleeding episodes***

Patients must report all bleeding episodes and bleed treatment in eDiaries when bleeds and treatment occur away from the investigational site. When occurring at the investigational site, circumstances of the bleed and the bleed treatment will be reported in the eCRF.

- Whenever recording a bleed in the eDiary, patients will receive a reminder on the eDiary device to contact investigator
- Investigator must report in the eCRF or eDiary-portal StudyWorks whether a patient-investigator contact was established before treating the bleed. The investigator must also report treatment type for each treatment
- Investigator is requested to perform a rating of the severity of each bleeding episode reported and report the severity in StudyWorks or in the eCRF as applicable

## Appendix 12 Flowcharts applicable for patients enrolled before the treatment pause and who have permanently discontinued treatment prior to restart

The below flowchart is only applicable for those patients enrolled in the trial before the treatment pause and who have permanently discontinued from treatment prior to restart. Patients who enrolled in the trial or reinitiated treatment after the treatment pause must follow the flowcharts in Section 2.

|                                                      | Main Part      |                |                |         |         |         |         |         |                |                  |          |          | Extension Part |          |          |          |          |          |          |          |          |          |          |          |          |          |          |          |
|------------------------------------------------------|----------------|----------------|----------------|---------|---------|---------|---------|---------|----------------|------------------|----------|----------|----------------|----------|----------|----------|----------|----------|----------|----------|----------|----------|----------|----------|----------|----------|----------|----------|
|                                                      | Visit 1        | Visit 2        | Visit 3        | Visit 4 | Visit 5 | Visit 6 | Visit 7 | Visit 8 | Visit 9        | Visit 9.1        | Visit 10 | Visit 11 | Visit 12       | Visit 13 | Visit 14 | Visit 15 | Visit 16 | Visit 17 | Visit 18 | Visit 19 | Visit 20 | Visit 21 | Visit 22 | Visit 23 | Visit 24 | Visit 25 | Visit 26 | Visit 27 |
| Visit                                                | 1 a | 2 b | 3 c | 4       | 5       | 6       | 7       | 8       | 9 b | 9.1 d | 10       | 11       | 12             | 13       | 14       | 15       | 16       | 17       | 18       | 19       | 20       | 21       | 22       | 23       | 24       | 25       | 26       | 27       |
| Timing of Visit (Weeks)                              | -3             | 0              | 1              | 4       | 8       | 12      | 16      | 20      | 24             | 25               | 32       | 40       | 48             | 56       | 64       | 72       | 80       | 88       | 96       | 104      | 112      | 120      | 128      | 136      | 144      | 152      | 160      | 167      |
| Visit Window (Days)                                  | ±0             | ±0             | ±1             | ±3      | ±3      | ±3      | ±3      | ±3      | ±1             | ±3               | ±3       | ±3       | ±3             | ±3       | ±3       | ±3       | ±3       | ±3       | ±3       | ±3       | ±3       | ±3       | ±3       | ±3       | ±3       | ±3       | ±3       | ±3       |
| SUBJECT RELATED INFORMATION AND ASSESSMENTS          |                |                |                |         |         |         |         |         |                |                  |          |          |                |          |          |          |          |          |          |          |          |          |          |          |          |          |          |          |
| Informed consent                                     | X              |                |                |         |         |         |         |         |                |                  |          |          |                |          |          |          |          |          |          |          |          |          |          |          |          |          |          |          |
| In/exclusion Criteria                                | X              | X              |                |         |         |         |         |         |                |                  |          |          |                |          |          |          |          |          |          |          |          |          |          |          |          |          |          |          |
| Demography                                           | X              |                |                |         |         |         |         |         |                |                  |          |          |                |          |          |          |          |          |          |          |          |          |          |          |          |          |          |          |
| Concomitant medication                               | X              | X              | X              | X       | X       | X       | X       | X       | X              | X                | X        | X        | X              | X        | X        | X        | X        | X        | X        | X        | X        | X        | X        | X        | X        | X        | X        |          |
| Concomitant illness                                  | X              |                |                |         |         |         |         |         |                |                  |          |          |                |          |          |          |          |          |          |          |          |          |          |          |          |          |          |          |
| Medical history                                      | X              |                |                |         |         |         |         |         |                |                  |          |          |                |          |          |          |          |          |          |          |          |          |          |          |          |          |          |          |
| Details of Haemophilia l                  | X              |                |                |         |         |         |         |         |                |                  |          |          |                |          |          |          |          |          |          |          |          |          |          |          |          |          |          |          |
| Haemophilia treatment and bleed history l | X              | X              |                |         |         |         |         |         |                |                  |          |          |                |          |          |          |          |          |          |          |          |          |          |          |          |          |          |          |
| Target Joints                                        | X              |                |                |         |         |         |         |         |                | X                |          |          |                |          |          |          |          |          |          |          |          |          |          |          |          |          |          |          |
| Treatment discontinuation criteria                   |                |                | X              | X       | X       | X       | X       | X       | X              | X                | X        | X        | X              | X        | X        | X        | X        | X        | X        | X        | X        | X        | X        | X        | X        | X        | X        |          |
| Withdrawal criteria                                  |                | X              | X              | X       | X       | X       | X       | X       | X              | X                | X        | X        | X              | X        | X        | X        | X        | X        | X        | X        | X        | X        | X        | X        | X        | X        | X        |          |
| Randomisation                                        |                | X              |                |         |         |         |         |         |                |                  |          |          |                |          |          |          |          |          |          |          |          |          |          |          |          |          |          |          |

|                                | Main Part      |                |                |         |         |         |         |         |                |                  |          |          | Extension Part |          |          |          |          |          |          |          |          |          |          |          |          |          |          |          |   |   |
|--------------------------------|----------------|----------------|----------------|---------|---------|---------|---------|---------|----------------|------------------|----------|----------|----------------|----------|----------|----------|----------|----------|----------|----------|----------|----------|----------|----------|----------|----------|----------|----------|---|---|
|                                | Visit 1        | Visit 2        | Visit 3        | Visit 4 | Visit 5 | Visit 6 | Visit 7 | Visit 8 | Visit 9        | Visit 9.1        | Visit 10 | Visit 11 | Visit 12       | Visit 13 | Visit 14 | Visit 15 | Visit 16 | Visit 17 | Visit 18 | Visit 19 | Visit 20 | Visit 21 | Visit 22 | Visit 23 | Visit 24 | Visit 25 | Visit 26 | Visit 27 |   |   |
| Visit                          | 1 a | 2 b | 3 c | 4       | 5       | 6       | 7       | 8       | 9 b | 9.1 d | 10       | 11       | 12             | 13       | 14       | 15       | 16       | 17       | 18       | 19       | 20       | 21       | 22       | 23       | 24       | 25       | 26       | 27       |   |   |
| Timing of Visit (Weeks)        | -3             | 0              | 1              | 4       | 8       | 12      | 16      | 20      | 24             | 25               | 32       | 40       | 48             | 56       | 64       | 72       | 80       | 88       | 96       | 104      | 112      | 120      | 128      | 136      | 144      | 152      | 160      | 167      |   |   |
| Visit Window (Days)            | ±0             | ±0             | ±1             | ±3      | ±3      | ±3      | ±3      | ±3      | ±1             | ±3               | ±3       | ±3       | ±3             | ±3       | ±3       | ±3       | ±3       | ±3       | ±3       | ±3       | ±3       | ±3       | ±3       | ±3       | ±3       | ±3       | ±3       | ±3       |   |   |
| EFFICACY                       |                |                |                |         |         |         |         |         |                |                  |          |          |                |          |          |          |          |          |          |          |          |          |          |          |          |          |          |          |   |   |
| Bleeding episode               |                |                | X              | X       | X       | X       | X       | X       | X              | X                | X        | X        | X              | X        | X        | X        | X        | X        | X        | X        | X        | X        | X        | X        | X        | X        | X        | X        |   |   |
| Body measurements e | X              | X              | X              | X       | X       | X       | X       | X       |                | X                | X        | X        | X              | X        | X        | X        | X        | X        | X        | X        | X        | X        | X        | X        | X        | X        |          |          |   |   |
| Thrombin generation            |                | X b | X              | X       | X       | X       | X       | X       | X b | X                | X        | X        | X              | X        | X        | X        | X        | X        | X        | X        | X        | X        | X        | X        | X        | X        | X        | X        |   |   |
| Sport activity                 |                | X              |                |         |         |         |         |         | X              |                  |          |          |                |          |          |          |          |          |          |          |          |          |          |          |          |          |          |          | X |   |
| Concizumab ELISA f  |                | X b | X              | X       | X       | X       | X       | X       | X b | X                | X        | X        | X              | X        | X        | X        | X        | X        | X        | X        | X        | X        | X        | X        | X        | X        | X        | X        |   |   |
| Free TFPI                      |                | X b | X              | X       | X       | X       | X       | X       | X b | X                | X        | X        | X              | X        | X        | X        | X        | X        | X        | X        | X        | X        | X        | X        | X        | X        | X        | X        |   |   |
| SAFETY                         |                |                |                |         |         |         |         |         |                |                  |          |          |                |          |          |          |          |          |          |          |          |          |          |          |          |          |          |          |   |   |
| Adverse event                  | X              | X              | X              | X       | X       | X       | X       | X       | X              | X                | X        | X        | X              | X        | X        | X        | X        | X        | X        | X        | X        | X        | X        | X        | X        | X        | X        | X        |   |   |
| Injection site reaction        |                | X              | X              | X       | X       | X       | X       | X       | X              | X                | X        | X        | X              | X        | X        | X        | X        | X        | X        | X        | X        | X        | X        | X        | X        | X        | X        | X        |   |   |
| ECG l               | X              |                |                |         |         |         |         |         |                |                  |          |          |                |          |          |          |          |          |          |          |          |          |          |          |          |          |          |          |   |   |
| Coagulation Parameters         | X              | X              | X              | X       | X       | X       | X       | X       | X              | X                | X        | X        | X              | X        | X        | X        | X        | X        | X        | X        | X        | X        | X        | X        | X        | X        | X        | X        |   |   |
| Coagulation factors            | X              |                |                |         |         |         |         |         |                |                  |          |          |                |          |          |          |          |          |          |          |          |          |          |          |          |          |          |          |   |   |
| Haematology                    | X              | X              | X              | X       | X       | X       | X       | X       | X              | X                | X        | X        | X              | X        | X        | X        | X        | X        | X        | X        | X        | X        | X        | X        | X        | X        | X        | X        |   |   |
| Biochemistry                   | X              | X              | X              | X       | X       | X       | X       | X       | X              | X                | X        | X        | X              | X        | X        | X        | X        | X        | X        | X        | X        | X        | X        | X        | X        | X        | X        | X        |   |   |
| Urinalysis                     | X              |                |                |         |         |         |         |         |                |                  |          |          |                |          |          |          |          |          |          |          |          |          |          |          |          |          |          |          |   |   |
| Physical examination           | X              | X              |                |         |         |         |         |         | X              |                  |          |          |                |          |          | X        |          |          |          |          |          | X        |          |          |          |          |          |          | X | X |
| Vital signs                    | X              | X              | X              | X       | X       | X       | X       | X       | X              | X                | X        | X        | X              | X        | X        | X        | X        | X        | X        | X        | X        | X        | X        | X        | X        | X        | X        | X        |   |   |
| Anti-concizumab antibodies     | X              | X              |                | X       | X       | X       | X       | X       | X              |                  |          | X        |                |          | X        |          | X        |          | X        |          | X        |          | X        |          | X        |          | X        | X        |   |   |

ONLY APPLICABLE FOR PATIENTS WHO HAVE RECEIVED TREATMENT  
PERMANENTLY DISCONTINUED OR RESTARTED

|                                             | Main Part      |                |                |         |         |         |         |         |                |                  |          |          | Extension Part |          |          |          |          |          |          |          |          |          |          |          |          |          |          |          |   |
|---------------------------------------------|----------------|----------------|----------------|---------|---------|---------|---------|---------|----------------|------------------|----------|----------|----------------|----------|----------|----------|----------|----------|----------|----------|----------|----------|----------|----------|----------|----------|----------|----------|---|
|                                             | Visit 1        | Visit 2        | Visit 3        | Visit 4 | Visit 5 | Visit 6 | Visit 7 | Visit 8 | Visit 9        | Visit 9.1        | Visit 10 | Visit 11 | Visit 12       | Visit 13 | Visit 14 | Visit 15 | Visit 16 | Visit 17 | Visit 18 | Visit 19 | Visit 20 | Visit 21 | Visit 22 | Visit 23 | Visit 24 | Visit 25 | Visit 26 | Visit 27 |   |
| Visit                                       | 1 a | 2 b | 3 c | 4       | 5       | 6       | 7       | 8       | 9 b | 9.1 d | 10       | 11       | 12             | 13       | 14       | 15       | 16       | 17       | 18       | 19       | 20       | 21       | 22       | 23       | 24       | 25       | 26       | 27       |   |
| Timing of Visit (Weeks)                     | -3             | 0              | 1              | 4       | 8       | 12      | 16      | 20      | 24             | 25               | 32       | 40       | 48             | 56       | 64       | 72       | 80       | 88       | 96       | 104      | 112      | 120      | 128      | 136      | 144      | 152      | 160      | 167      |   |
| Visit Window (Days)                         | ±0             | ±0             | ±1             | ±3      | ±3      | ±3      | ±3      | ±3      | ±1             | ±3               | ±3       | ±3       | ±3             | ±3       | ±3       | ±3       | ±3       | ±3       | ±3       | ±3       | ±3       | ±3       | ±3       | ±3       | ±3       | ±3       | ±3       | ±3       |   |
| FVIII/FIX inhibitors                        | X              |                |                |         |         |         |         |         |                |                  |          |          |                |          |          |          |          |          |          |          |          |          |          |          |          |          |          |          | X |
| Total TFPI                                  |                | X              | X              | X       | X       | X       | X       | X       | X              | X                | X        | X        | X              | X        | X        | X        | X        | X        | X        | X        | X        | X        | X        | X        | X        | X        | X        | X        |   |
| OTHER ASSESSMENTS                           |                |                |                |         |         |         |         |         |                |                  |          |          |                |          |          |          |          |          |          |          |          |          |          |          |          |          |          |          |   |
